5.2 Evaluations During Study

Table 3 Monitoring

	Pre Study (within 3 days of consent)	Week 1-12 (every 2 wks)###	Post Completion of study drug**
CBC, Na, K, Cl, CO ₂ , ALT, Bili, Alk Phos, albumin, tot protein, BUN & creatinine	X	X	X
PT/PTT	X		X
Thrombopoietin	X		X
PK Studies		X^^	
Toxicity assessment (history and PE) (Graded per NCI toxicity criteria)	X	X	X
Bone Marrow (incl reticulin and collagen staining)	X#		X^
B-HCG pregnancy test in women of child- bearing age	X##		
No. of Platelet & RBC transfusions	X (in the 4 wks prior to study entry)	X	X
Immune Reconstitucional Studies ***	X		X
Ophthalmic Evaluation	X ⁺		X ⁺⁺

A previous biopsy done within one year is acceptable for baseline purposes and a separate bone marrow biopsy will not be required. To assess for fibrosis, special staining for reticulin and collagen will be performed.

Negative pregnancy test is required prior to receiving drug but is not required prior to consent.

Visits at Week 10 and 12 will done by telephone interview and blood work can be drawn locally.

^ First routine bone marrow done after study completion for assessment of disease status will be stained for reticulin and collagen to assess fibrosis. The bone marrow will be performed within 3 months after the last dose of study drug.

^^ No PK studies will be drawn for weeks 10 and 12.

** Date of last dose of study drug.

+ Within 6 months of study entry.

** Within 3 months of last dose of study drug. This will be done earlier if patients develop visual symptoms indicative of cataract.

*** Peripheral blood T-cell subsets, NK and B-cell immune reconstitution

Note: All assessments to be done within 3 days of stated time point.

Statistical Considerations:

Overview

This will be a randomized, double-blind Phase II trial to compare eltrombopag and placebo in patients with thrombocytopenia post transplant. The primary endpoint will be development of a platelet count $\geq 30 \times 10^9/l$ by day 57 without platelet transfusion.

Adaptive Randomization

We will use a Bayesian adaptive algorithm (Berry, 1994) to randomize patients between the two treatment arms. The first 20 patients will be randomized fairly (i.e. fixed allocation of 1:1) between the two arms, after which the response adaptive randomization will begin. As the trial progresses and data accrue, the randomization will become unbalanced in favor of the treatment that, on average, has better results in terms of response, so that each successive patient is more likely to receive the treatment showing better results.

The randomization algorithm based upon this method will be implemented by using the Clinical Trial Conduct website developed by the Department of Biostatistics at M.D. Anderson Cancer Center.

The target enrollment for the study is a maximum of 64 patients, and we expect to enroll an average of 2 patients per month. We will follow all patients until they go off study. We assume a Beta(0.4, 1.6) prior distribution for the probability of response in each arm. We use the following notation: We denote the response rate in the placebo arm as R_p , and the response rate in the eltrombopag arm as R_E . We then denote P_p as the probability that the response rate in the placebo arm is greater than the response rate in the eltrombopag arm. Formally,

$$P_p = \text{Prob}(R_p > R_E \mid \text{data from patients evaluated at day 57}) \text{ and} \\ P_E = 1 - P_p = \text{Prob}(R_E > R_p \mid \text{data from patients evaluated at day 57})$$

The trial will be stopped early and eltrombopag (placebo) selected as being superior if at any time during the course of the trial $P_p > 0.98$ (< 0.02). If the trial is not stopped early and all 64 patients are enrolled and evaluated at day 57, then eltrombopag will be declared superior (inferior) if $P_p > 0.975$ (< 0.025).

After the first 20 patients are randomized fairly, patients will be randomized to the eltrombopag arm with probability $\max(0.20, P_p)$ and to the placebo arm with probability $\max(0.20, P_e)$. In other words, randomization probabilities are subject to the constraint that the minimum randomization probability to either arm is 20%.

The primary endpoint is development of a platelet count $\geq 30 \times 10^9/l$ at day 57 without platelet transfusion within 7 days. Patients who drop out of the trial before completion of day 57 with a platelet count $\geq 30 \times 10^9/l$ at the time of discontinuation will be considered successes with respect to the primary endpoint.

Patients who drop out of the study after being randomized but before receiving any study drug will not be included in the analysis and will be replaced. All patients who receive a single dose of study drug will be included in the analysis.

Safety Monitoring

Patient safety will be monitored during this trial by reviewing the rate of development of toxicity, relapse, and mortality.

If a patient develops a grade 3 or higher toxicity attributed to the drug, the study drug will be stopped in that patient. This may be recommenced at the discretion of PI after resolution of the toxicity and review of the data.

For grade 4 toxicity, the PI will routinely review patient data and will temporarily halt the study pending study team review if a high rate of unexpected grade 4 toxicity is noticed. The case report form used for data collection will be PDMS/CORE.

We will use a formal Bayesian monitoring rule to monitor the rate of death or relapse on this study. We wish to ensure that the rate of death/relapse at day 57 is no more than 30% in either study arm. If there is a high probability that this rate is greater than 30% in either arm, we will temporarily halt and review the data with the MDACC IRB and FDA before continuing.

The method of Thall, Simon, and Estey will be employed separately in each arm to perform this monitoring. We will assume a noninformative Beta(0.6, 1.4) distribution on the prior probability that a patient experiences death or relapse, which has a mean of 30% but carries little prior information. We will start monitoring with the first patient in each arm and will use the following rule: halt accrual onto an arm if at any time during the course of the study:

$$\Pr\{57\text{-day death/relapse on the arm} > 30\% \mid \text{data from patients evaluable at day 57}\} > 0.925$$

In other words, if at any time during the trial, we determine that there is greater than a 92.5% chance that the 57-day death/relapse in an arm is greater than 30%, we will temporarily halt the arm pending IRB and FDA review.

This rule leads to the following stopping boundaries: halt the trial if the number of patients that have died/relapsed in an arm out of the number of patients evaluable at day 57 in that arm is $\geq 2/2, 3/3, 4/5, 5/7, 6/8, 7/12, 8/14, 9/17, 10/20, 11/22, 12/25, 13/28, 14/31, 15/33, 16/36, \text{ and } 17/39$. If a decision to stop depends upon data from patients that have been enrolled but who have not yet reached day 57, accrual will temporarily be halted until enough patients are evaluable as to be able to reach this decision. Anticipated study enrollment is 1-2 patients per week, but as an additional safety measure, first 4 patients will be enrolled at a minimum interval of two weeks between consecutive patients.

Joint Operating Characteristics of Adaptive Randomization and Safety Rules
(See table in protocol.)

Analysis Methods
(Details in protocol.)

Where Will Participants Be Enrolled:

Only at MDACC

Is this an NCI-Cancer Therapy Evaluation Protocol (CTEP)? No

Is this an NCI-Division of Cancer Prevention Protocol (DCP)? No

Estimated Accrual:

Total Accrual at MDACC: 64
Estimated monthly accrual at MDACC: 2

Accrual Comments:

Do you expect your target population to include non-english speaking participants? Yes

Please select expected languages of non-English speaking participants. (Select all that apply)
Expected languages of non-English speaking participants:

Spanish

Location of Treatment:

This protocol is performed on an Outpatient basis.

Length of Stay: What is the length & frequency of hospitalization?

N/A

Return Visits: How often must participants come to MDACC?

Every 2 weeks for first eight weeks during the period of active treatment

Home Care: Specify what, if any, treatment may be given at home.

1) Observation without any treatment from week 9 to 12 and 2) Open label phase after week 12 if patient chooses to enrol in it.

Name of Person at MDACC Responsible for Data Management: [[name]](#)

Prior protocol at M. D. Anderson:

Has the Principal Investigator ever had a clinical or behavioral protocol at MDACC that accrued patients?
Yes

Data Monitoring Committee:

Is treatment assignment randomized? Yes

Is this a blinded or double-blinded study? Yes

Does this Protocol need data safety monitoring? Yes

Provide the name of the data safety monitoring board (DSMB) monitoring this protocol:
MDACC DMC

Does this protocol have a schedule for interim and final analysis? Yes

Please describe:
Bayesian adaptive design

Radiation Safety:

Does this study involve the administration of radioisotopes or a radioisotope labeled agent?	No
Is the radioactive compound (or drug) FDA approved and/or commercially available?	No

Investigational New Drugs:

Does this protocol require an IND? Yes
Please list the IND holder and provide the IND number:

IND Holder: [MDACC](#)
IND Number: [106,182](#)

Investigational Device:

Is the Investigational Device approved by the FDA? N/A

Is the Investigational Device being used in the manner approved by the FDA? N/A

Has the Investigational Device been modified in a manner not approved by the FDA? N/A

Name of Device: N/A

Manufacturer: N/A

What is the FDA Status of the Investigational Device? Not Marketed.

Is the study being conducted under an Investigational Device Exemption (IDE)? No

IDE Holder: N/A

IDE Number: N/A

Risk Assessment:

Please answer the following questions regarding the Investigational Device.

Intended as an implant? No

Purported or represented to be for use supporting or sustaining human life? No

For use of substantial importance in diagnosing, curing, mitigating, or treating disease, or otherwise preventing impairment of human health? No

You may attach sponsor documentation of the risk assessment:

Will participant be charged for the Investigational Device? No

Sponsorship and Support Information:

Does the Study have a Sponsor or Supporter? Yes

Sponsor or Supporter: Novartis Pharmaceuticals Corporation

Type(s) of Support: Funds

Agent

Monitored by Sponsor or Sponsor Representative (CRO)? No

Is this Protocol listed on any Federal Grant or Foundation Funding Application? No

Biosafety:

Does this study involve the use of Recombinant DNA Technology? No

Does this study involve the use of organisms that are infectious to humans? No

Does this study involve stem cells? No

Technology Commercialization:

Does this study include any agents or devices manufactured or produced at MD Anderson Cancer Center? No

Laboratory Tests:

Where will laboratory tests be performed on patient materials? (Please select all that apply)
Division of Pathology & Laboratory Medicine CLIA Certified Laboratory

Other

Please provide the name of the test(s), the purpose of the test, and the performing laboratory identification and contact information.

1) Thrombopoietin assay : To check thrombopoietin levels pre and post treatment.

R & D systems
[name]
Key Account Manager
R&D Systems, Inc.
[name]
Department 371

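### Does an early superiority stop leave open which patients decide the result, those evaluated at day 57 or all those dosed?

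*Combined protocol and SAP*

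**What the plan says.** All the relevant text is under Statistical Considerations.

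- **Early stop (Adaptive Randomization).** "The trial will be stopped early and eltrombopag (placebo) selected as being superior if at any time during the course of the trial" the posterior passes 0.98 or 0.02. The posterior is defined as conditional on "data from patients evaluated at day 57".
- **Full enrolment (same section).** The 0.975/0.025 cut-off is introduced by "If the trial is not stopped early and all 64 patients are enrolled and evaluated at day 57".
- **Follow-up (same section).** "We will follow all patients until they go off study".
- **Analysis set (end of the same section, just before Safety Monitoring).** Patients who leave after randomization without taking study drug are excluded and replaced. Then: "All patients who receive a single dose of study drug will be included in the analysis".
- **Pending patients (Safety Monitoring).** After the death/relapse boundaries, a clause beginning "If a decision to stop depends upon data from patients that have been enrolled but who have not yet reached day 57" pauses accrual until enough patients are evaluable.
- **Deferred material.** Analysis Methods says only "Details in protocol". The item headed "Joint Operating Characteristics of Adaptive Randomization and Safety Rules" points to a table that is not in the supplied text.
- **Accrual.** Adaptive Randomization and Estimated Accrual give 2 patients per month. Safety Monitoring gives 1 to 2 per week.

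**The concern.** The endpoint takes 57 days and accrual continues, so some dosed patients are nearly always pending when the efficacy rule fires. They are followed and they belong to the analysis set, so their outcomes arrive after a winner has been selected. The efficacy text does not say what happens if those outcomes pull the posterior back. The pause for pending patients sits with the safety rule and does not mention superiority.

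Three readings therefore seem possible:

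- **A.** The selection is final at the crossing.
- **B.** Enrolment ends, but the selection stands only if all dosed patients still support it.
- **C.** Accrual pauses at the crossing, and the trial resumes if the posterior falls back once the pending patients are evaluated.

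If the plan were truly silent, the reading could be picked after the late outcomes were known. Error rate and power would then depend on that choice.

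**Working it through.** The supplied text gives no power or false-selection rate for the efficacy rule, so there is no stated figure to reproduce.

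**Inputs from the plan.** Beta(0.4, 1.6) prior in each arm; at most 64 patients; first 20 at 1:1, then adaptive with a 20% floor; early cut-offs 0.98/0.02; final cut-offs 0.975/0.025; outcome at day 57; first 4 patients at least two weeks apart. The plan defines its posterior symbol as placebo being better but selects eltrombopag when that symbol is high. The evident intent is used here: eltrombopag is selected when P(R_E > R_P) is high.

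**Assumptions.** The response rates (50% vs 20%, and 20% in both arms) are not in the plan; 20% is only the prior mean, 0.4/(0.4 + 1.6). A look is taken after every evaluated patient, which the wording of the early-stop rule permits. Safety halts and dropouts are not modelled.

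**Step 1: patients pending at a crossing.** Accrual rate × 57 days:

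- 2 per month: 57 × 2/30.4 = 3.75
- 1 per week: 57/7 = 8.1
- 2 per week: 57 × 2/7 = 16.3

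The simulated averages are about 3 to 4, 8 and 15.

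**Step 2: one example.** With x responders among n, each arm's posterior is Beta(0.4 + x, 1.6 + n − x).

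- 17 evaluated, 5/8 on eltrombopag vs 1/9 on placebo: Beta(5.4, 4.6) vs Beta(1.4, 9.6), P(R_E > R_P) = 0.986. This is above 0.98, so eltrombopag is selected.
- Three pending patients finish 1/2 and 1/1, giving 6/10 vs 2/10: Beta(6.4, 5.6) vs Beta(2.4, 9.6), P(R_E > R_P) = 0.964. This is below both cut-offs.

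**Step 3: how often this happens.** Share of early selections whose posterior on all dosed patients is back inside 0.975/0.025, by Monte Carlo with the 57-day lag:

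| True response | 2 per month | 1 to 2 per week |
|---|---|---|
| 50% vs 20% | 22-23% | 23-26% |
| 20% vs 20% | 31-33% | 46-61% |

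Separate programs gave 21-27% for the first row and values from 28% upward for the second. The second row is a share of the 23-25% of equal-arm trials that stop early. At 2 per month that is between 0.31 × 0.23 = 7% and 0.33 × 0.25 = 8% of all trials. If looks began only after 20 evaluated patients, the shares over all accrual rates would be about 13-17% and 26-55%.

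**Step 4: how far the posterior falls.** At 50% vs 20%, only 8-12% of early selections drop below 0.95. In one run at 2 per month, 3% dropped below 0.90 and essentially none below 0.50. The selected arm still looks better in nearly every case.

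**Step 5: what each reading would give at 2 per month.**

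| Reading | Eltrombopag selected, 50% vs 20% | Mean enrolment, 50% vs 20% | False selection, 20% vs 20% |
|---|---|---|---|
| A | 80-81% | 34-35 | 23-25% |
| B | 62-63% | 34-35 | 15.5-17% |
| C | 75% | 40 | 17% |

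**Step 6: which reading the text supports.** The early-stop sentence joins stopping and selecting in one act and names the data used. The only other efficacy cut-off is conditional on there having been no early stop. That is reading A. Reading B needs a second test that appears nowhere in the supplied text. Reading C needs the pending-patient clause to be moved from the death/relapse rule, where it stands, to the superiority rule.

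**The case for a change.** The strongest case for a change is that the stakes are not small. At 2 per month and 50% vs 20%, readings A and B differ by 80 − 62 = 18 points of power. With equal arms they differ by about 8 points of false selection, and by more at faster accrual. The authors saw that pending patients matter for the safety rule, yet wrote nothing on them beside the efficacy rule. Two sentences would remove any doubt, and the accrual figures that determine the number pending disagree.

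Part of this stands. The arithmetic is right. The supplied text does not say how late outcomes are to be reported after an early selection, and the accrual figures are inconsistent.

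It does not show a missing decision rule. The differences in power and error arise only if B or C is a live reading, and the supplied text supports neither. The sentence on dosed patients separates those who took study drug from those who never did. An interim decision and a later report on all treated patients can coexist. The yardstick also matters: 0.975/0.025 is the full-enrolment cut-off, so falling inside it does not reverse an early selection under any written rule. The accrual discrepancy alters how many patients are pending, but no decision rule. The deferred analysis section may also cover the reporting.

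**Conclusion.** No change to the plan is called for. Read as written, an early selection is final at the crossing and rests on patients evaluated at day 57. The later outcomes belong to the report on all dosed patients, which the analysis-set sentence already implies. A competent analyst would show that result beside the one at the crossing.

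The two posteriors can differ noticeably: about 22-26% of early selections at 50% vs 20%, and about 28-61% of the 23-25% that stop early with equal 20% arms, end back inside a cut-off the plan does not apply to them. These figures rest on assumed response rates, looks from the first evaluated patient, and accrual anywhere from 2 per month to 2 per week.

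Writing down reading A would leave error, power and enrolment as they are. Reading B would give up 17 to 19 points of power at 50% vs 20% and 2 per month. Reading C would give up 5 to 6 points and enrol about 5 to 6 more patients on average. Both also lower false selection, so each is a trade-off open to the sponsor, not a correction the plan needs. How often the rule selects wrongly when the arms are equal is a separate question from which data set decides.

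### The efficacy stopping, final decision and allocation rules use P_p (probability that placebo is better) where P_E is needed, so as written they favour the worse arm

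*Combined protocol and SAP*

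**What the plan says.** All the relevant text is in the combined protocol and SAP, under Statistical Considerations, Adaptive Randomization.

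- **Labels:** "We denote the response rate in the placebo arm as R_p , and the response rate in the eltrombopag arm as R_E".
- **Definition in words:** the authors "denote P_p as the probability that the response rate in the placebo arm is greater than the response rate in the eltrombopag arm".
- **Definition by formula:** "P_p = \text{Prob}(R_p > R_E \mid \text{data from patients evaluated at day 57"}) and "P_E = 1 - P_p = \text{Prob}(R_E > R_p \mid \text{data from patients evaluated at day 57"}).
- **Early stopping:** "eltrombopag (placebo) selected as being superior if at any time during the course of the trial $P_p > 0.98$ (< 0.02").
- **Final decision at 64 patients:** "eltrombopag will be declared superior (inferior) if $P_p > 0.975$ (< 0.025").
- **Allocation after the first 20 patients:** "patients will be randomized to the eltrombopag arm with probability $\max(0.20, P_p)$ and to the placebo arm with probability $\max(0.20, P_e").
- **Purpose of the adaptation:** the imbalance is meant to work "so that each successive patient is more likely to receive the treatment showing better results".

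No other section of the supplied text restates or corrects these rules. The joint operating characteristics and the analysis methods are left to a fuller protocol.

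**The concern.** By definition a large P_p means placebo is ahead. The three rules read a large P_p as evidence for eltrombopag. The definition and the rules cannot both be right, and the allocation rule also contradicts the stated purpose of the adaptation.

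In the supplied text these are the only rules that decide the primary comparison. Anyone who programs, monitors or re-analyses the trial from this text would reverse its conclusion and, after the 20-patient lead-in, send most patients to the inferior arm. The trial is double-blind, so a reversed imbalance would not be obvious to those treating patients.

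A lesser point concerns the allocation pair. As printed, the two probabilities do not sum to 1 once either posterior probability falls below 0.20.

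**Working it through.** **Direction of the rules.** This step needs no assumed rates. The definition gives P_E = 1 − P_p.

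| Rule | As written | Same condition in terms of P_E | Meaning |
|---|---|---|---|
| Stop for eltrombopag | P_p > 0.98 | P_E < 0.02 | stops for eltrombopag when it is almost surely worse |
| Stop for placebo | P_p < 0.02 | P_E > 0.98 | stops for placebo when it is almost surely worse |
| Final: eltrombopag superior | P_p > 0.975 | P_E < 0.025 | reversed |
| Final: eltrombopag inferior | P_p < 0.025 | P_E > 0.975 | reversed |
| Allocation to eltrombopag | max(0.20, P_p) | max(0.20, 1 − P_E) | falls as eltrombopag does better |

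**Worked data sets.** The inputs are the plan's Beta(0.4, 1.6) prior in each arm and its thresholds; the responder counts are illustrative. With x responders among n patients, the posterior is Beta(0.4 + x, 1.6 + n − x). P_p is found by numerical integration over the two independent posteriors.

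- Placebo 1/10, Beta(1.4, 10.6), against eltrombopag 6/10, Beta(6.4, 5.6): P_p = 0.0087 and P_E = 0.9913. Since 0.0087 < 0.02, the text stops and selects placebo.
- The same data with the arms exchanged: P_p = 0.9913 > 0.98, so the text selects eltrombopag.
- Placebo 3/32, Beta(3.4, 30.6), against eltrombopag 12/32, Beta(12.4, 21.6), with all 64 patients evaluated: P_p = 0.0032 < 0.025, so eltrombopag is declared inferior.
- Placebo 2/10 against eltrombopag 6/10: P_p = 0.0358. Eltrombopag gets max(0.20, 0.0358) = 0.20. Placebo gets max(0.20, 0.9642) = 0.964, or 0.80 if capped.

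**Simulated size.** The supplied text gives no design response rates, so all true rates here are assumptions. The maximum of 64 patients, the 1:1 lead-in of 20, the priors and the thresholds are the plan's. Allocation was held within 0.20 to 0.80.

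Simulation A used 2,500 trials with about 4 patients awaiting outcome at any time.

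| True rate, eltrombopag v placebo | Literal: placebo named | Literal: eltrombopag named | Patients after the 20th on eltrombopag, literal | Same, corrected |
|---|---|---|---|---|
| 50% v 20% | about 78% | about 0.5% | about 25% | about 75% |
| 40% v 20% | about 54% | about 1.5% | about 29% | about 71% |

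Simulation B used 1,000 trials per setting, with outcomes known at once, looks after every patient from the 20th, and no safety stopping.

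| True rate, eltrombopag v placebo | Rules | Eltrombopag named | Placebo named | All patients on eltrombopag |
|---|---|---|---|---|
| 50% v 20% | literal | 0.0% | 74.7% | 38.0% |
| 50% v 20% | corrected | 77.7% | 0.1% | 61.8% |
| 30% v 10% | literal | 0.2% | 59.9% | 37.9% |
| 30% v 10% | corrected | 59.6% | 0.2% | 62.2% |
| 20% v 20% | literal | 8.6% | 7.6% | 51.1% |
| 20% v 20% | corrected | 9.3% | 9.1% | 50.0% |

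The allocation shares in A and B have different denominators but agree. At 50% v 20%, the mean sample size in B was 39.4 with the literal rules. Eltrombopag patients: 0.380 × 39.4 = 15.0, of whom 10 came from the lead-in. After the 20th patient: (15.0 − 10) / (39.4 − 20) = 5.0 / 19.4, about 26%. With the corrected rules the mean was 38.3: (0.618 × 38.3 − 10) / (38.3 − 20) = 13.7 / 18.3, about 75%. With equal true rates the two orientations behave alike within simulation error, as they should.

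**Allocation sum.** If one posterior probability is q > 0.80, the pair sums to q + 0.20.

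- q = 0.85: 1.05
- q = 0.90: 1.10
- q = 0.95: 1.15
- q = 0.98: 1.18

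Rescaling to total 1 at q = 0.95 gives the minority arm 0.20 / 1.15 = 17.4%, below the stated 20% minimum.

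**The case against.** The best defence is that this is a slip of notation. The intent is plain from the same section, a statistician would see the swap, and harm follows only if someone applies the letter of the text against its purpose. Randomization runs on the institution's trial-conduct website, and nothing shows that its arms were labelled the wrong way round. This stands as a limit: the finding concerns the written plan, not the conduct of the trial. It does not excuse the text, because the decision rules are what a programmer or re-analyst works from.

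The fuller protocol, to which the operating characteristics and analysis methods are deferred, may state the rules correctly. That also stands as a limit of scope. It would leave two conflicting statements to reconcile.

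A misread subscript is possible in text extracted from PDF, and the allocation rule does print P_e where the definition prints P_E. But the definition is also given in words, and all three rules are reversed. One misreading cannot explain that.

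On the allocation sum, the plan states a 20% minimum for either arm. With two arms this implies an 80% maximum, and rescaling is mentioned nowhere. This objection largely succeeds: the point is a minor drafting matter.

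Finally, the simulated percentages depend on assumed response rates and, in Simulation B, on ignoring the safety stops. That is true, but the direction of the error follows from the definitions alone.

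**Conclusion.** The concern holds. As written, the early-stopping, final-decision and allocation rules are all reversed relative to the plan's own definition of P_p. The reversal is certain from the text; its size depends on the true rates. At an assumed 50% v 20% in favour of eltrombopag, the literal rules name placebo superior in about 75% to 78% of trials and eltrombopag in 0% to 0.5%, and give eltrombopag to about 25% of patients after the 20th instead of about 75%. At 40% v 20%, placebo is still named in about 54%. These figures assume allocation capped at 0.80. Whether the reversal reached the randomization software or any decision cannot be told from the supplied text. The correction is essential because these rules determine the trial's conclusion; the allocation sum is a minor addition.

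**What to change.** Replace P_p with P_E in the decision rules and rewrite the allocation pair:

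- **Early stopping:** eltrombopag if P_E > 0.98; placebo if P_E < 0.02.
- **Final decision:** eltrombopag superior if P_E > 0.975; inferior if P_E < 0.025.
- **Allocation after patient 20:** eltrombopag with probability min(0.80, max(0.20, P_E)); placebo with one minus that.

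Exchanging the two definitions instead would correct the direction of all three rules in one edit, but would leave the p subscript on the probability that eltrombopag is better. Make one change or the other, since both together would restore the error. The 0.80 cap should be written out either way.

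Then check the website's configuration against the corrected text. The version is marked as terminated on 04/16/2018, so the check should cover the allocations already made, any stopping decision and the reported result, and the orientation actually used should be documented. The fuller protocol should be checked for the same wording.

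The cost is a change of wording and one check of the software. No threshold, sample size or study procedure changes.
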